9.4.3 ANALYSIS OF THE SECONDARY ENDPOINT(S)

Qualitative Analysis of Implementation:

Qualitative interviews will be transcribed from audio recordings, with personal identifiers removed. Pairs of researchers trained in qualitative analysis will analyze transcripts in Dedoose using a combination of content-analysis and qualitative inquiry, allowing them to discover and quantify the nurses' experiences and perceptions. We will use an iterative process to identify *a priori* themes based on the domains above, and to create *in vivo* themes as they emerge during coding (e.g., specific barriers to implementation).⁶⁵ The two coders will code each interview independently and then discuss variations until consensus is reached. After coding all interviews, we will use the constant comparative method to combine similar themes with limited data under more general themes.⁶⁶ In the final step of analysis, we will review Dedoose code reports (participant N and density) of salient themes and coding matrices related to significant interview findings.

9.4.4 SAFETY ANALYSES

Nurses:

- The Analytical Team will monitor responses to a relevant domain on the AHRQ Hospital Survey on Patient Safety Culture, Nonpunitive Response to Error, which reflects whether nurses feel that they have been blamed for reported incidents. This survey will be deployed before and after the implementation of the SAFE Loop, enabling the research team to detect problems with the first implementation phase before the subsequent phase begins.
- [name] will meet periodically with nursing unit managers to qualitatively monitor nurses' perceptions of the study, including whether they have any concerns or any potential or actual adverse events have occurred.
- [name] will monitor for qualitative increases in the number of referrals of nurses to the Human Resources Department on the intervention nursing units during the study period.

Patients:

- [name] will work with the Cedars-Sinai Patient Safety Department, which handles incident reports, to qualitatively monitor whether there may be any reports addressing risks to patients associated with changes in practice on study nursing units that were implemented in response to the intervention.

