2.3 RISK/BENEFIT ASSESSMENT

2.3.1 KNOWN POTENTIAL RISKS

There are two categories of study subjects who will be affected by SAFE Loop:

1. **Nurses** and nursing unit managers who work in the nursing units, and
2. **Patients** who receive care there.

Table of Study Procedures and Associated Risks for Each Group.

Study Procedure	Risks for Nurses	Risks for Patients
1. Organizational Quality Improvement Intervention: Implementation of SAFE Loop in nursing units	Psychological distress or loss of professional reputation may occur if a nurse is blamed for a medication error after an incident report is submitted. Risks are similar to those in usual nursing practice because nurses already submit incident reports.	Medication error. Risks are unlikely but may occur if the nursing units inadvertently implement changes that worsen rather than improve medication safety, as intended.

	To further mitigate the risks, we will train nurses to emphasize reporting of near misses and no-harm events (which are less likely to result in punitive responses by unit managers) and train unit managers in the “just culture” approach, which emphasizes changing systems of care rather than blaming individual nurses when medication errors occur.	
2a. Research data collection: nursing work schedules, to assess nurse eligibility for survey	Inadvertent disclosure of individually identifiable information on nursing work schedules. This data source does not include sensitive information.	Not applicable.
2b. Research data collection: surveys of nurses on attitudes toward reporting and patient safety culture	Inadvertent disclosure of individually identifiable information on nursing survey. Survey does not involve sensitive information and it is already routinely deployed in this hospital.	Not applicable.
3. Research data collection: analysis of incident reports to assess rate and quality of reports	Inadvertent disclosure of individually identifiable information. This data source includes sensitive information such as errors that nurses may have committed. Data to be extracted will not include individually identifiable information about nurses.	Inadvertent disclosure of protected health information (PHI). Incident reports contain patient identifiers and PHI. Data to be extracted will not contain patient identifiers aside from randomly assigned study identification numbers to facilitate linkage to other datasets.

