2.3.2 KNOWN POTENTIAL BENEFITS

Nurse participants: Nurses may benefit from the SAFE Loop intervention through improvements in their skill in reporting medication errors; such reporting is considered a basic responsibility in nursing practice. Additionally, participation may enhance professional satisfaction, because the nurses on each study unit come together to choose a medication safety problem to solve and then help to collect useful information on that problem by filing incident reports. The intervention is also designed to improve the reporting culture at the institution, shifting from a culture that may blame reporters for events to a culture that uses reports as tools for improving systems of care.

Patient participants: Patients may benefit from the SAFE Loop intervention through reductions in rates of medication errors. Additionally, improved incident reporting systems may help to lower the rates of harmful medication errors at the study hospital.

Society: If effective, the research will demonstrate a strategy for improving patient safety in hospitals through the use of incident reporting. In the future, hospitals that implement the SAFE Loop may experience several benefits: increasing nurses’ engagement with reporting, collecting more informative reports, enabling safety leaders to understand problems and design system-based solutions more effectively and more efficiently, and lowering rates of medication errors. In turn, receiving feedback about problems and system-based solutions will further improve nurses’ perceptions of reporting. In addition to the local benefits to hospitals, these changes will create secondary benefits nationally by enhancing the functioning of AHRQ Patient Safety Organizations, which rely on incident reports as critical sources of insights into safety concerns in hospitals and potential solutions.

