The survey takes 10-15 minutes to complete and includes 42 items used to derive 12 composite measures (**Table 8**), 2 single-item measures, and respondents' backgrounds (unit, staff position, interaction with patients, years of experience in current profession, hospital, and current nursing unit). Most items are scored on a scale from 1 (strongly agree) to 5 (strongly disagree). Creating composite scores involves: (1) inverting the scales of any negatively worded items, (2) identifying positive responses (1 or 2); (3) calculating the percent of responses that were positive for each item (excluding missing values), and (4) averaging the percent positive across all items within a composite measure.

The two composite measures we plan to use are directly relevant to incident reporting and likely to be responsive to system-level changes. *Feedback and Communication About Error* includes three items: staff are informed about errors, discuss ways to prevent errors, and are given feedback about changes implemented. The *Frequency of Events Reported* also includes three items: staff report mistakes that are caught before affecting the patient, with no potential to harm, and that could harm but did not. In a prior analysis from three nursing units at three different hospitals, scores on these two composite measures were correlated ($\rho=0.56$) but factor analyses indicated that they captured distinct concepts (loaded separately). Respectively, Cronbach α values for these measures were 0.77 and 0.78 among nurses, demonstrating good internal consistency.⁵⁵

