B. Data Collection: Cedars-Sinai routinely surveys staff every two years using the Hospital SOPS. For the study, we will survey ~1980 eligible nurses on study nursing units twice via 4 total deployments of the full Hospital SOPS during two-week intermissions between study periods (Section 3A). To identify eligible nurses, we will obtain staffing databases including names, email addresses, title/position, percent effort, dates of work on the unit, and work schedule. At least 85% of nurses on study units will be eligible. Two weeks before deployment, we will send email notices to expect the survey and a researcher will visit nursing units to reinforce survey completion. The survey will be delivered via REDCap using a weblink embedded in an email. During each deployment, we will deliver the survey three times. We will incentivize completion at the individual (lotteries for iPads) and unit levels (gift baskets of snacks for response rates >65%). To minimize detection bias, the survey will not refer to the SAFE Loop intervention. To avoid having incomplete outcome data, we will monitor survey response rates and make adjustments to procedures as needed.

Methods for Aim 3: Rates of Target Medication Events

A. Measures: The primary outcome will be the *rate per 1,000 patient-days of Target Medication Events (preventable plus potential adverse drug events)* selected by the 10 nursing units in Groups 1 and 3. We will also examine the rate of events involving harm. We will define events as in prior research (**Table 10**).^{38,61,62}

Table 10: Medication Event Definitions		Examples
ADE (NCC MERP severity E-I)	A patient injury* resulting from a medical intervention related to drug(s).	A rash due to an antibiotic.
Preventable	An adverse drug event due to a medication error. †	A rash due to an antibiotic given despite known allergy.
Non-preventable	An adverse drug event not due to an error.	A rash occurring after first exposure to an antibiotic.
Potential ADE	A medication error that had the potential to cause injury but did not.	
Intercepted (NCC MERP B)	A medication error that was detected and stopped before the patient received the medication.	A pharmacist filling orders discovers a known allergy and prompts the prescriber to switch antibiotics.

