9.4.2 ANALYSIS OF THE PRIMARY EFFICACY ENDPOINT(S)

Aim 1 Analyses:

Descriptive Analysis: We will perform descriptive analyses of reporting practices during the baseline periods and intervention periods, stratified by study arm. We will calculate rates of reported Target Medication Events and total reported medication events per 1000 patient-days (# of reports*1000/# of patient-days). Next, we will calculate the percentages of reported incidents in each NCC MERP category and the percentages of reports for which preventability could be determined. Finally, we will calculate

the number of contributing system, human, and patient factors per report and describe the types of factors reported.

Statistical Analyses: We will compare changes over time between study arms for: (a) rate of incident reports per 1000 patient-days, and (b) number of system plus human factors per report. Multivariable Poisson regression models will be fitted with response variables as (a) number of reports per patient, with offset given by the length of stay divided by 1000; and (b) number of system plus human factors per report. For both models, the main hypothesis is whether there is an interaction between study arm and time period (baseline, post-intervention). Nursing units will be divided between two implementation steps, creating the possibility of an implementation trend. Therefore, a three-way interaction among study arm, time period, and implementation step (Step 1: Group 1 and 2, Step 2: Group 3 and 4) will be tested. If this is statistically significant, results will be presented separately for each implementation step. Otherwise, implementation step will be an additive effect. Random effects will describe nursing units and models will adjust for demographics, Elixhauser comorbidity index, and primary payer (collected under Aim 3). All hypotheses will be two-sided at 5% significance level. Calculations will be performed in R-package, version 3.5.3.

Aim 2 Analyses:

Descriptive Analysis: We will calculate survey response rates, examine respondent characteristics (years worked in current profession, hospital, and current nursing unit and hours worked per week), and describe outcome measures (overall scores and composite measures) during each study period, stratified by study arm.

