Assessment of Survey Measurement Properties: To evaluate the two selected composite measures' internal consistency, we will calculate Cronbach's α using data from baseline survey. To assess construct validity and convergent validity, respectively, we will evaluate associations (Pearson correlation coefficients) between scores on the composite measures and: (1) the full Hospital SOPS, and (2) incident reporting rates at the nursing unit level. To assess responsiveness, we will compare scores from baseline and follow-up surveys among nurses in the SAFE Loop arm (paired t-tests). If the composite measures do not demonstrate good internal consistency, construct, and convergent validity, we will use the full Hospital SOPS.

Statistical Analyses: We will compare changes over time between study arms for Feedback and Communication About Error and Frequency of Events Reported. Multivariable Normal regression models will be fitted for both endpoints and we will test hypotheses similarly to Aim 1. We will adjust for nurse characteristics from the AHRQ survey: years working in this hospital, years worked in current nursing unit, and hours worked per week. We will perform subgroup analyses by years of experience in current profession, because experience has been associated with medication error rates.⁵⁹

Aim 3 Analyses:

Descriptive Analysis: We will calculate rates of preventable ADEs and potential ADEs per 1,000 patient-days, both overall and for the Target Medication Events for the Group 1 and 3 nursing units. We will describe the severity of the events, medication classes, errors, clinicians involved, and stages in drug therapy.

Statistical Analysis: We will compare changes over time between study arms for rates of (a) Target Medication Events per 1000 patient-days and (b) harmful Target Medication Events per 1000 patient-days. Multivariable Poisson models will be fitted with response variable as the number of (a) target medication events and (b) harmful medication events, with offset the length of stay divided by 1000

days. We will test hypotheses similarly to under Aim 1. Model covariates will include patient demographics, biological sex, Elixhauser comorbidity index, and insurance payer.

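### Nonpunitive Response to Error is surveyed before and after in both randomised arms, but no between-arm difference in change with a cluster-adjusted interval is planned

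*Combined protocol and SAP*

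**What the plan says.** Section 2.3.1 lists blame as a risk to nurses: "Psychological distress or loss of professional reputation may occur if a nurse is blamed for a medication error after an incident report is submitted". Section 2.3.2 expects the opposite as a benefit, "shifting from a culture that may blame reporters for events to a culture that uses reports as tools for improving systems of care".

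Section 9.4.4 gives three nurse safety measures.

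- The survey domain: "The Analytical Team will monitor responses to a relevant domain on the AHRQ Hospital Survey on Patient Safety Culture, Nonpunitive Response to Error".
- Periodic qualitative meetings with unit managers.
- HR referrals, for which a study leader "will monitor for qualitative increases in the number of referrals of nurses to the Human Resources Department on the intervention nursing units".

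On collection, section 8.1 says "we will survey ~1980 eligible nurses on study nursing units twice via 4 total deployments of the full Hospital SOPS". The design table in 6.3 shows baseline and follow-up surveys in the control groups (2 and 4) as well as the SAFE Loop groups (1 and 3).

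On analysis, the Aim 2 text in 9.4.2 says: "We will compare changes over time between study arms for Feedback and Communication About Error and Frequency of Events Reported". Nonpunitive Response to Error is not among these. The Aim 2 model follows Aim 1, where "Random effects will describe nursing units". The Aim 2 descriptive paragraph covers composite measures by period and arm. Section 8.2 sends the responses on this domain to the external monitor after each deployment. Section 9.3 says that analyses compare the two arms.

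**The concern.** Blame could move either way. The intervention prompts more reporting, which could expose nurses, and it also trains managers in just culture. Of the three nurse measures in 9.4.4, this domain is the only one stated to be collected before and after in both arms. The HR item is watched on intervention units, and the manager meetings are qualitative. The domain is therefore the one measure that can separate a SAFE Loop effect on blame from a hospital-wide shift.

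Monitoring responses does not make that separation. By-arm means, if they are tabulated, would let a reader compute a difference in change. With only 20 clusters, the reader would not know how much of it could be chance. The trial would then end without a randomised estimate, with its uncertainty, for a harm that it names.

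**Working it through.** **1. Is the estimate already planned?** Section 9.3 defines which data are compared and gives no model. The descriptive paragraph in 9.4.2 gives no contrast and no interval. The model paragraph names two other composites. The fallback to the full survey in 9.4.2 would replace those two and would not isolate blame. The answer is no.

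**2. The plan's own inputs (9.2, Aim 2).** Responses per unit per deployment: 1980 × 0.85 × 0.60 / 20 = 50.49, which reproduces the stated 50.5. The SD of a uniform score on 0, 33, 66 and 100 is 37.2, which agrees with the stated 37.

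**3. Precision of the missing estimate.** With k units per arm, m responses per unit per wave and between-wave unit correlation c:

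Var(difference in change) = (2/k) × [2·SD²·(1 − ICC)/m + 2·SD²·ICC·(1 − c)]

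Half-width = t(0.975, 2k − 2) × square root of the variance.

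Example with k = 10, SD 37, m = 50.49, ICC 0.05, c = 0.8:

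- First term: 2 × 1369 × 0.95 / 50.49 = 51.52.
- Second term: 2 × 1369 × 0.05 × 0.2 = 27.38.
- Variance: 0.2 × 78.90 = 15.78, so SE = 3.97.
- Half-width: 2.101 × 3.97 = 8.3 pp.

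95% half-widths in pp for 10 v 10 units, SD 37, no repeat respondents:

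| c | ICC 0.01 | 0.05 | 0.10 | 0.20 |
|---|---|---|---|---|
| 1 | 6.9 | 6.7 | 6.6 | 6.2 |
| 0.8 | 7.2 | 8.3 | 9.6 | 11.6 |
| 0.5 | 7.7 | 10.3 | 12.8 | 16.7 |
| 0 | 8.5 | 12.9 | 16.9 | 22.8 |

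Ignoring clustering gives 6.5 pp throughout.

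**4. Sensitivity.** The documents give no SD, ICC or c for this domain, and the SD of 37 is derived for three-item composites. At the site's 35% positive (Table 8) the SD cannot exceed √(35 × 65) = 47.7 pp. That scales every entry by 47.7/37 = 1.29, to 8.0–8.9 at c = 1 and 9.3–15.0 at c = 0.8. Repeat respondents work the other way. As an illustration, assume 80% overlap and a within-nurse correlation of 0.5. The sampling term is then multiplied by 1 − 0.8 × 0.5 = 0.6, and the c = 1 row falls to 4.8–5.3 (√0.6 = 0.775).

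**5. Step 1 alone (5 v 5, 8 df).** Half-widths are 9.6–10.7 pp at c = 1 and 11.2–18.0 at c = 0.8.

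**6. Which random effects.** This bears only on how to specify the added model. In simulation with no true effect (4000 runs per cell, 20 units, 50 responses per unit per wave), a unit random intercept alone rejected in 11% (ICC 0.05) and 19% (ICC 0.10) of runs at c = 0.8, and in about 5% at c = 1. Comparing unit-level changes on 18 df stayed at 4.4–5.3% in every cell.

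**The case against.** The strongest case against is that the gap is small. Manager meetings, HR-referral monitoring, serious adverse event reporting and external review all remain, and section 10.1.6 argues for proportionate oversight of a low-risk intervention. If the descriptive paragraph covers this domain, only a contrast and its interval are missing. Section 9.4.4 also uses the survey to find problems before the second phase starts, and an end-of-trial model cannot serve that purpose. A separate Data and Safety Monitoring Plan might say more about how the responses are presented. All of this limits the point to end-of-trial safety reporting. None of it supplies the missing estimate.

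Two technical objections stand. Nurses are surveyed twice and paired tests are planned, so treating respondents as independent between waves overstates the half-widths. The simulation results depend on a correlation that the documents do not give, and they do not measure the harm of omitting the analysis.

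A reader might infer that a null result could not rule out a meaningful worsening. The figures do not support that. What an interval excludes depends on its half-width, and 8 of the 16 entries in the table are below the plan's 8.6 pp benchmark. In those cases an estimate near zero would exclude a worsening of that size.

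A reader might also infer selective reporting from the choice of two other composites. The plan gives its reason: "The two composite measures we plan to use are directly relevant to incident reporting and likely to be responsive to system-level changes".

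**Conclusion.** The point holds as a modest improvement to safety reporting. The domain is collected before and after in both arms, and the plan describes or forwards it without estimating the randomised difference in change with an interval that allows for clustering. The estimate would have a half-width of about 6–7 pp at between-wave unit correlation 1, 7–12 at 0.8 and 8–17 at 0.5. These figures assume that the Aim 2 SD and ICC range apply to this domain and that no nurse responds twice. Overlapping respondents would narrow them and a larger SD would widen them. The 8.6 pp benchmark comes from overall survey scores, so it is only a guide for this domain. The interval may or may not exclude a worsening of that size, and a wide one is not evidence of no harm. By-arm figures after step 1 are a screen only. No efficacy conclusion changes, and the documents do not suggest that nurses are left unmonitored.

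**What to change.** Add to section 9.4.4:

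> At the end of the trial, the SAFE Loop minus control difference in change in Nonpunitive Response to Error will be estimated from all 20 nursing units. The estimate will come from a comparison of unit-level changes (t interval, 18 df, or 17 if adjusted for implementation step) or from the Aim 2 arm-by-period Normal model with random effects for nursing unit and for nursing unit by period. It will be reported with a 95% confidence interval as a safety estimate outside the efficacy hypotheses, and a wide interval will not be read as evidence of no harm. Responses sent to the DSM after each deployment will be shown by arm, descriptively.

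The unit-by-period term is needed because 9.4.2 names only nursing-unit random effects. The cost is a short paragraph, one extra analysis and an arm split of data already sent to the external monitor. No new data or staff are needed. The downside is one more result whose interval may be wide.

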8.2 SAFETY AND OTHER ASSESSMENTS

The level and frequency of monitoring are designed to be commensurate with the risks, nature, and complexity of this clinical trial. Additionally, the data safeguarding procedures will adhere to all current standards established under the Common Rule, the Health Insurance Portability and Accountability Act (HIPAA), policies by AHRQ and NIH, and policies established by the Cedars-Sinai Institutional Review Board. All investigators have undergone required trainings in human subjects' protections and have extensive experience in handling sensitivity information. As PI, [name] has ultimate responsibility for monitoring data and safety.

Monitoring procedures will serve the following functions: (1) reviewing the research protocol and plans for data and safety monitoring issues; (2) monitoring data quality, timeliness, survey response rates, and factors that may affect the risks and benefits of the study such as emerging literature; (3) monitoring for potential and actual adverse events, and (4) making recommendations regarding continuation of the trial.

Internal Monitoring Procedures: The study team will learn of potential issues with data and safety for nurses and patients through the following procedures.

Nurses: [name] will meet periodically with nursing unit managers to qualitatively monitor nurses' perceptions of the study, including whether they have any concerns or any potential or actual adverse events have occurred. As Chief Patient Safety Officer, [name] will monitor for increases in the number of referrals of nurses to the Human Resources Department on the intervention nursing units during the study period. Additionally, the Analytical Team will monitor responses to a relevant domain on the AHRQ Hospital Survey on Patient Safety Culture, Nonpunitive Response to Error, which reflects whether nurses feel that they have been blamed for reported incidents. This survey will be deployed before and after the implementation of the SAFE Loop, enabling the research team to detect problems with the first implementation phase before the subsequent phase begins.

Patients: [name] will work with the Cedars-Sinai Patient Safety Department, which handles incident reports, to qualitatively monitor whether there may be any reports addressing risks to patients associated with changes in practice on study nursing units that were implemented in response to the intervention.

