Inadvertent Disclosures of Identifiable Information: The team will self-monitor whether data are collected, stored, transmitted, and analyzed in accordance with the Data and Safety Monitoring Plan and for any inadvertent disclosures of sensitive information.

The research team will include data and safety monitoring on the agenda of each routine team meeting, enabling any concerns to be identified and addressed quickly. The study will submit annual progress reports to the Cedars-Sinai Institutional Review Board and meet annually with the external DSM during Years 1 to 4.

External Monitoring Procedures: The DSM will monitor throughout the portions of the study that involve human subjects, including implementation of the SAFE Loop, surveys of nurses, and extraction of data from incident reports and medical records. The DSM will meet with the Executive Oversight Team four times via teleconference to review the Data and Safety Monitoring Plan, proposed study procedures, data safeguarding practices, and data on potential and actual adverse events.

- *Year 1:* The DSM will meet to review study protocols and the Data and Safety Monitoring Plan prior to the start of data collection.
- *Year 2:* The DSM will meet to monitor progress in the study and consider any new information related to risks to nurse and patients. This meeting will represent a project milestone (see timeline) because it will provide a more complete picture of the risks associated with the study.
- *Year 3:* The DSM will meet to monitor progress and any potential or actual adverse events. Additionally, the study Analytical Team will send the external monitoring body the survey responses on Nonpunitive Responses to Error after each deployment of the survey.
- *Year 4:* The DSM will meet after the intervention and data collection are complete to review information on potential or actual adverse events. This meeting will represent a project milestone (see timeline) because it will be the concluding meeting of the DSM.
- *Additional Reviews:* The DSM will reserve the right to request additional interim reviews, in the unlikely event that concerns are raised about data safeguarding or safety.

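### HR referrals, the only listed count close to the job-consequence SAEs, are to be watched on intervention units alone, so this count by itself cannot tell a SAFE Loop effect from a hospital-wide change

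*Combined protocol and SAP*

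**What the plan says.** Section 9.4.4 lists three nurse items, in this order.

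1. A survey domain: "The Analytical Team will monitor responses to a relevant domain on the AHRQ Hospital Survey on Patient Safety Culture, Nonpunitive Response to Error".
2. Contact with managers: the responsible team member "will meet periodically with nursing unit managers to qualitatively monitor nurses' perceptions of the study".
3. Human Resources referrals: the responsible team member "will monitor for qualitative increases in the number of referrals of nurses", limited to the intervention units. The scope is given as "referrals of nurses to the Human Resources Department on the intervention nursing units during the study period".

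Section 8.2 has the same restriction and gives the task to the Chief Patient Safety Officer, who is to "monitor for increases in the number of referrals of nurses to the Human Resources Department on the intervention nursing units". The word qualitative appears only in 9.4.4. Neither section names a control-unit count, a baseline count, a denominator or a threshold.

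The survey is different: "we will survey ~1980 eligible nurses on study nursing units twice via 4 total deployments of the full Hospital SOPS". It therefore covers both arms before and after implementation, and the Analytical Team "will send the external monitoring body the survey responses on Nonpunitive Responses to Error after each deployment of the survey". Section 9.3 says that every analysis compares the two arms.

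**The concern.** Section 2.3.1 names blame after an incident report, with distress or loss of reputation, as the nurse risk of the intervention. Section 8.3.1 makes adverse job consequences serious adverse events: adverse documentation in employment files, reduced hours, lost opportunities, dismissal. Of the three nurse signals, only the referral count comes close to recording such consequences rather than perceptions or conversations.

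The direction of any change is hard to predict. The SAFE Loop stimulates reporting, which could raise referrals, and trains managers in just culture, which could lower them (Section 6.1.1). Without concurrent controls, a rise in the count may only reflect a hospital-wide change, and a flat count may conceal a SAFE Loop increase offset by a hospital-wide fall. The judgement is also unstructured, and it falls to the officer who oversees implementation (Section 6.4). A control-arm count would give that judgement an objective reference.

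**Working it through.** **No figure to reproduce.** The documents give no referral count, rate, threshold, alpha or power.

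**Is a comparator available?** The unit table in Section 5.1 lists 20 units in 5 blocks of four. The nurse numbers sum to 1,980, as stated. Section 6.3 assigns two of four units per block to each arm, so an arm averages 1,980 / 2 = 990 nurses. The smallest possible arm takes the two smallest units in each block: 195 + 91 + 178 + 160 + 131 = 755. The largest is 1,980 − 755 = 1,225. A concurrent control group exists at the same hospital, but the arms may differ enough in size that counts should be expressed per nurse.

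**What each design identifies.** Let g be the hospital-wide ratio of referral rates between periods and s the SAFE Loop ratio.

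- Intervention units, after / before: g × s
- Control units, after / before: g
- Ratio of the two: s

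With only the first line there is one quantity and two unknowns. A value of 1.5 fits s = 1.5 with g = 1, and equally s = 1 with g = 1.5.

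**Illustration; every input is assumed.** Poisson counts with mean m per arm at baseline and m × g afterwards, equal arms, s = 1, 200,000 runs, one-sided 5% tests. Here a0 and a1 are the intervention counts before and after, and c0 and c1 the control counts; 0.5 is added to each count.

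- Intervention only: z = [log a1 − log a0] / √(1/a1 + 1/a0)
- With controls: z = [log a1 − log a0 − log c1 + log c0] / √(1/a1 + 1/a0 + 1/c1 + 1/c0)

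Probability of a false signal (z > 1.645), intervention only / with controls:

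| m | g = 1.0 | g = 1.5 | g = 2.0 |
|---|---|---|---|
| 5 | 0.029 / 0.038 | 0.132 / 0.039 | 0.315 / 0.039 |
| 10 | 0.040 / 0.045 | 0.235 / 0.046 | 0.557 / 0.047 |
| 20 | 0.045 / 0.048 | 0.395 / 0.048 | 0.825 / 0.048 |
| 40 | 0.048 / 0.048 | 0.635 / 0.049 | 0.979 / 0.049 |

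The plan specifies no such test. The table shows only how far an uncontrolled before-after comparison can mislead, and it ignores clustering by unit.

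**Precision with controls.** With 10 referrals in each of the four cells, the standard error of log s is √(4/10) = 0.63, so 95% limits span a factor of exp(1.96 × 0.632) = 3.45 either way. With 40 per cell it is √(4/40) = 0.32 and a factor of 1.86. Adding controls removes the confounding but does not make the count a sensitive test.

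**The case against.** **The survey already gives a controlled signal.** A reader might infer that HR referrals are the main nurse-harm signal. The documents do not support that. They come last of three items, and the nurse signal specified for the external monitor after each deployment is the survey domain, which has both arms. This stands. However, the survey records the perceptions of respondents, with 60% response assumed (Section 9.2). Eligibility requires more than half-time work on one unit over a six-month period (Section 5.1), so a dismissed nurse may be absent at follow-up. The follow-up deployment also precedes the follow-on period (Section 6.3).

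**Case review separates causes.** A reader might also infer that the monitoring system as a whole cannot separate SAFE Loop harm from background change. That goes too far. Section 8.2 requires suspected events to be investigated for attribution to the study. Sections 8.3.2.2 and 8.3.3 add a relatedness judgement, including a link in time to a Target Medication Event report on an intervention unit. Nurse SAEs are individual events with 24-hour reporting (Section 8.3.5), so their detection does not depend on a net change in a count. This also stands, but reviewing cases does not show whether the referral rate moved relative to controls.

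**Some comparator may be implicit.** An increase presupposes an earlier level, and Section 1.3 lists baseline among the study periods. The Section 6.3 table, as extracted, also shows Group 3 in baseline while Group 1 is in SAFE Loop. Neither comparison is specified for referrals, Group 3 is identified only when its envelope is opened, and a within-unit baseline does not remove a hospital-wide change.

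**Monitoring is meant to be proportionate.** Section 8.2 says so, and Section 10.1.6 argues that risk is low. Referrals feed no endpoint, hypothesis or stated stopping rule. That limits the importance of the point, but does not justify leaving out a control count.

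**Conclusion.** The point holds in a narrow form. Sections 8.2 and 9.4.4 both state the restriction to intervention units, so this is a written rule and not missing detail. It yields an uncontrolled count although 10 randomised control units run concurrently at the same hospital, and it sits awkwardly with Section 9.3. The claim concerns this count alone; the survey and the case-level review offset the gap in part.

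The size of the problem cannot be derived from the documents. The false-signal probabilities rest wholly on assumed counts, an assumed hospital-wide shift, Poisson variation and a formal test that the plan does not use. The algebra needs none of these. Severity is low: no efficacy conclusion is affected, and the correction is an improvement to safety monitoring.

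**What to change.** In Sections 8.2 and 9.4.4, extend the referral item from the intervention units to all 20 study nursing units. State that referrals are counted by one definition and from one source in the baseline, implementation and follow-on periods. Provide the external monitor with descriptive counts per nurse, by arm and period, alongside the survey domain. Say that the counts are a prompt for case review and not a powered comparison.

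Counting all units from the start also means that baseline collection for Groups 3 and 4 does not depend on knowing their allocation, which stays sealed until their implementation period begins.

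Cost: the same count for 10 more units. This assumes that referral counts for control units are as accessible as those for intervention units; the documents do not describe the HR data source. Small counts will limit precision, and the text should say so.
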